3.2 Exclusion Criteria

Patients are not eligible if any one of the following conditions exists:

- 1) Carcinoma in situ or invasive cancer on baseline endobronchial biopsy.
- 2) A malignancy except for adequately treated basal cell or squamous cell skin cancer or in situ cervical cancer.
- 3) Severe lung disease or inability to undergo two bronchoscopies.
- 4) Had pneumonia or acute bronchitis within the past 2 weeks prior to the date of enrollment (i.e., signing the consent form).
- 5) Had myocardial infarction (MI) or other severe heart diseases such as ventricular tachycardia, multifocal premature ventricular contractions or supraventricular tachycardias with a rapid ventricular response within the past 6 weeks prior to enrollment.
- 6) Hypoxemia (less than 90% saturation with supplemental oxygen).

- 7) Prior chemotherapy or thoracic radiation within the past 5 years.
- 8) Woman who is pregnant or plan to be pregnant in next 12 months, or is breast feeding or plan to begin breast feeding in next 12 months.
- 9) Life expectancy of < 12 months.
- 10) Have a history of irritable bowel disease such as Crohn's disease and ulcerative colitis.

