3.1 Eligibility Criteria

- 1) Man or woman 55-74 years of age.
- 2) Patients with normal endobronchial biopsy findings or pre-cancerous lesions at baseline will be eligible for the study. Pre-cancerous lesions include (a) reserve cell hyperplasia, (b) squamous metaplasia, (c) mild dysplasia, (d) moderate dysplasia, and (e) severe dysplasia.
- 2) A former smoker who has a history of smoking with ≥ 30 pack-years, quits smoking within the past 10 years, and has more than 1 year sustained abstinence from smoking.
- 3) Female subjects must be of non-child bearing potential or must have a negative urine pregnancy test at screening (within 72 hours of first dose of study medication) if of childbearing potential.
- 4) Male and female subjects of childbearing potential must be willing to use adequate barrier methods of contraception from the time starting with the screening visit through 30 days after the last dose of study therapy.
- 5) Abstinence is acceptable if this is the established and preferred contraception for the subject.
- 6) Generally healthy with liver enzyme and blood count values within the ranges shown below on the blood sample drawn at the baseline screening visit.
Specifically:

White blood cells	$\geq 3,000/\text{mL}$
Total bilirubin	$\leq 1.5 \times \text{ULN}$ (upper limits of normal)
AST (SGOT)/ALT (SGPT)	$\leq 2.5 \times \text{ULN}$
BUN and serum creatinine	$\leq 1.5 \times \text{ULN}$
- 7) The presence of airflow obstruction on spirometry (GOLD 1-4 & $\text{FEV1}/\text{FVC} < 0.7$ & $\text{FEV1} < 0.8$) COPD; and/or any emphysema on CT scan.
- 8) Participants must have a Southwest Oncology Group (SWOG) performance status of 0-2 (Appendix 10).
- 9) Participants must be able and willing to undergo a bronchoscopy before and after treatment for 12 months.
- 10) Patients must be fully informed of the investigational nature of this study and must sign an informed consent in accordance with institutional and regulatory guidelines.

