3.4 Consent Procedure

At the screening clinical visit (stage 1-visit 1), a clinical research nurse practitioner and/or the project manager will go over with the study subjects about the study, eligibility criteria, procedures, and potential risk and benefits in participating in the study in a setting that is quiet and unhurried. The project manager will go over the written informed consent form with the study subject and answer any questions the patient may have. The authorization describes in detail what information, including the HIPPA-protected information, will be collected and for what purposes it will be used. A copy of signed consent will be provided to subject.

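### Exclusions 4 and 5 count their infection and cardiac windows back from signing consent, so an event between consent and the later baseline bronchoscopy meets neither

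*Combined protocol and SAP*

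**What the plan says.** Section 3.2, exclusion 4: "Had pneumonia or acute bronchitis within the past 2 weeks prior to the date of enrollment (i.e., signing the consent form". Exclusion 5, the next item, covers myocardial infarction and other severe heart disease, ending with "supraventricular tachycardias with a rapid ventricular response within the past 6 weeks prior to enrollment". It does not repeat the definition of enrollment.

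Section 3.4 places the consent discussion as follows: "At the screening clinical visit (stage 1-visit 1". Section 5.5 describes two stage 1 visits for eligibility screening. Section 5.1 requires a bronchoscopy before randomization and asks for pretreatment tests within 90 days before it. The list there includes both signed consent (item 1) and the baseline bronchoscopy (item 8). No other limit on the interval between them is given.

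Three other criteria bear on fitness for the procedure and carry no look-back period: inclusion 9 ("Participants must be able and willing to undergo a bronchoscopy before and after treatment for 12 months"), exclusion 3 ("Severe lung disease or inability to undergo two bronchoscopies") and exclusion 6 (hypoxemia).

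**The concern.** A look-back window protects a procedure only if it ends at that procedure. These two windows end at consent, which comes before the baseline bronchoscopy. Someone who develops pneumonia the day after signing, and has the bronchoscopy a week later, does not meet exclusion 4. The same holds for a cardiac event under exclusion 5.

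What is at stake is the safety of a research procedure in people selected for lung disease: inclusion 7 asks for "The presence of airflow obstruction on spirometry" and/or emphysema on CT. Section 7.1.2.1 lists a temporary fall in blood oxygen of about 10%, pneumonia and cardiac irregularity among the risks of bronchoscopy. Section 3.5 says that participants gain no health benefit from taking part. The protocol does not state what the windows are for, but protecting the bronchoscopy is a reading that these risks support.

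**Working it through.** The plan gives no figure on this point to reproduce. The check is of the order of events, followed by simple arithmetic on assumed inputs.

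**1. Order of events.** Consent is at stage 1 visit 1 (3.4). Bronchoscopy is a later stage 1 step before randomization (5.1, 5.5). The study calendar (section 6) appears to place it one column after consent. The extracted table is broken, but its compensation row of \$50 then \$500 agrees with section 3.5, which pays \$50 per clinic visit and \$500 per research bronchoscopy. The gap can therefore run from a few days to nearly 90.

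**2. Coverage.** Let g be the days from consent to bronchoscopy and W the window (14 for exclusion 4, 42 for exclusion 5). Of the W days before the procedure, min(g, W) fall after consent and are not covered. At g = 7 that is 7 of 14 days for infection and 7 of 42 for cardiac events. At g of 14 or more, exclusion 4 covers none of the fortnight before bronchoscopy. At g of 42 or more, exclusion 5 covers none of its six weeks.

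**3. Does the repeated form help?** The calendar marks the inclusion/exclusion form at three pre-treatment points, apparently including the bronchoscopy visit. Exclusion 4 as worded gives the same answer each time, because its reference date stays at consent. The bronchoscopy log in Appendix 9 is described in 7.1.2.1 as a follow-up tool for after the procedure.

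**4. Number of people.** Expected participants = 72 × annual rate × min(g, W)/365. The 72 is the planned randomized number. Rates and gaps are assumptions, because the documents give neither.

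| Event | Assumed rate per person-year | Gap | Expected of 72 |
|---|---|---|---|
| Chest infection | 0.1 to 1.0 | 7 days | 72 × 0.1 × 7/365 = 0.14 to 72 × 1.0 × 7/365 = 1.38 |
| Chest infection | 0.1 to 1.0 | 14 days or more | 72 × 0.1 × 14/365 = 0.28 to 72 × 1.0 × 14/365 = 2.76 |
| Cardiac event | 0.01 to 0.05 | 7 days | 72 × 0.01 × 7/365 = 0.01 to 72 × 0.05 × 7/365 = 0.07 |
| Cardiac event | 0.01 to 0.05 | 42 days or more | 72 × 0.01 × 42/365 = 0.08 to 72 × 0.05 × 42/365 = 0.41 |

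Somewhat more than 72 people may have a baseline bronchoscopy, because exclusion 1 ("Carcinoma in situ or invasive cancer on baseline endobronchial biopsy") removes some only after it.

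**5. Scale of harm.** Section 7.1.2.1 gives serious complications below 0.05%. Over 72 baseline procedures that is fewer than 72 × 0.0005 = 0.036 events. This is a general rate, not one for people who were recently ill.

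**6. Pretreatment time after a deferral.** Days left = 90 − elapsed gap − deferral, with consent taken on the first day of the span. A 14-day gap and 14-day deferral leave 90 − 14 − 14 = 62. A 42-day gap and 42-day deferral leave 90 − 42 − 42 = 6.

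**The case against.** The strongest case is that these windows are entry criteria, and that fitness for the procedure is left to clinical judgment. Consent falls at the visit where the calendar appears to place spirometry, oxygen saturation and blood tests, so an infection window dated to that visit makes sense for eligibility testing. The month-12 bronchoscopy carries the same listed risks and has no such window. Inclusion 9 and exclusions 3 and 6 have no reference date and can be judged on the day, and a co-principal investigator performs the procedure in a hospital endoscopy suite. The counts above are of exposure, not harm: 2.76 people at a rate below 0.05% is under 2.76 × 0.0005 = 0.0014 serious complications.

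Much of this stands. The purpose of the windows is unstated, the protection of screening spirometry is plausible, and an actively ill person would probably be deferred. But none of these provisions looks back 2 or 6 weeks. The protocol chose explicit windows for these conditions, and as dated they do not reach the bronchoscopy.

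A reader might infer that exclusion 5 leaves enrollment undefined, or that it means registration under section 3.6. The documents do not support this. Exclusion 4 defines the word one line earlier, and section 3.6 does not use it.

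**Conclusion.** The point holds as a minor patient-safety matter. Exclusion 4 is dated to consent by its own words, and exclusion 5 by the natural reading. Neither catches an event between consent and the baseline bronchoscopy. Under the assumed rates and gaps, about 0 to 3 of 72 participants would have a chest infection in the uncovered days, and fewer than 1 a cardiac event.

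Two stronger readings go too far. A reader might infer that recently ill people would simply be passed through to bronchoscopy, or that the protocol shows a raised complication risk in them. The undated criteria and clinical judgment give partial cover, and section 7.1.2.1 gives only general risks. A reader might also infer damage to the trial's results. There is no effect on power, alpha or bias; the gap lies wholly before randomization, so it cannot depend on the assigned arm.

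**What to change.** Reword exclusions 4 and 5 so that the existing 2-week and 6-week periods are counted back from the date of the baseline bronchoscopy. If exclusion 4 is also meant to protect the screening spirometry, keep the consent date there as a second reference point. Reconfirm both items on the existing inclusion/exclusion form at the bronchoscopy visit, and defer the procedure if either is met.

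The cost is a wording change in two criteria, one confirmation on a form already in use, and a few deferrals: about 0 to 3 for chest infection and fewer than 1 for a cardiac event, under the assumptions above. The pretreatment time left depends on the gap already elapsed (62 of 90 days in the 14-day case, 6 in the 42-day case). Some pretreatment tests may therefore need repeating, mainly after a cardiac deferral.

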3.3 Recruitment Methods

Patients for this trial will be recruited primarily from the participants of the Pittsburgh Lung Screening Study (PluSS) at the UPMC Hillman Cancer Center. This unique high-risk PluSS cohort enrolled approximately 3,600 current and former smokers in Pittsburgh area. The initial contact with the eligible subjects for the proposed study will be mailed a letter, followed up by a telephone call made by PluSS staff members who will briefly explain to the study subjects about the clinical trial and complete an eligibility screening form. Alternatively Any patients who are interested in participating in the study can telephone the clinical investigation office at [contact] Monday through Friday, 9:00 am to 5:00 pm (Eastern Time). The clinical research assistant will conduct a telephone interview with the potential study participant using the Eligibility Screening Form (Appendix 1). If all the requirements are met, the clinic research assistant will mail the following documents for subject to review before she or he has a scheduled clinical visit:

- 1) Locator Form (Appendix 2)
- 1) The Informed Consent Form (Appendix 3).
- 2) Baseline Medical History Questionnaire (Appendix 4).
- 3) Questionnaire for Cruciferous Vegetables (Appendix 5)

3.4 Consent Procedure

At the screening clinical visit (stage 1-visit 1), a clinical research nurse practitioner and/or the project manager will go over with the study subjects about the study, eligibility criteria, procedures, and potential risk and benefits in participating in the study in a setting that is quiet and unhurried. The project manager will go over the written informed consent form with the study subject and answer any questions the patient may have. The authorization describes in detail what information, including the HIPPA-protected information, will be collected and for what purposes it will be used. A copy of signed consent will be provided to subject.

3.5 Patient Payment

Subjects will receive no health benefit from participating in this research study. If SF is approved to be chemopreventive, subjects assigned to treatment arm may have some chemopreventive benefit from Avmacol®. Subjects will receive \$500 for each research bronchoscopy at baseline and at the end of the treatment. In addition, we will pay participants \$50 for each of 6 scheduled clinical visits from stage 1-visit 1 to stage 2-visit 6 to cover their costs of transportation and making effort to participate in the study. Parking for all clinical visits will be provided free of charge to the study

participants. At the end of the study treatment, the subject will receive \$500 as bonus for the compliance and completion of the study (see Appendix 6. Participant Compensation Form).

3.6 Registration Process

After being deemed eligible, participants will be assigned a patient number and be registered into the CTMA database.

4. STUDY AGENT INFORMATION

4.1 Broccoli seed preparations (BSP)

4.1.1 Summary

Broccoli seed preparations (BSP) have been studied extensively in multiple Phase I and Phase II clinical trials without Grade 2 or higher adverse effects. Broccoli seeds contain high concentrations of glucoraphanin (GR), the glucosinolate precursor of sulforaphane (SF), which is converted to SF by the release of intrinsic seed myrosinase during chewing or by thioglucosidaes in the microbiota in the human gut (25-27). The isothiocyanate SF (1-isothiocyanato-4R-(methylsulfinyl)butane) was originally isolated from commercial broccoli, and is one of the most potent naturally-occurring inducers of cytoprotective enzymes identified to date (28). SF activates the KEAP1-NRF2 signaling pathway, thereby increasing transcription of antioxidative and detoxication genes. For example, SF has been shown to induce cytoprotective enzymes in a variety of animal and human cell lines and tissues (29).

In our initial clinical trials, we investigated BSP in the form of re-hydrated, previously lyophilized broccoli sprout powders rich in either GR or SF produced by the Cullman Chemoprotection Center at Johns Hopkins under the supervision of Drs. [name] and [name]. Broccoli sprouts (*Brassica oleracea*) were grown from specially selected BroccoSprouts™ seeds to provide a consistent yield of GR or SF. In our initial trial, the GR-rich powder was considered as a food by the Johns Hopkins IRB. It is simply the freeze-dried powder derived from a hot water extract of broccoli sprouts. In 2010, the US FDA made a determination that beverages containing SF-rich broccoli sprout powders (but not GR-rich broccoli sprout powders) must be considered as drugs because the SF is formed ex vivo from the plant by the addition of myrosinase-containing daikon seeds during the preparation of the SF-rich powder. Thus, subsequent trials in Qidong, China (NCT01437501) as well as the pilot study at the University of Pittsburgh (NCT 02023931) have been conducted with an IND from the FDA (#112038) held by [name] PhD (Co-I).

There are three main problems in achieving consistent delivery and bioavailability of active SF by means of lyophilized broccoli sprout extracts: (1) SF is only moderately storage- and heat-stable over time, especially in aqueous solution. (2) SF-rich broccoli sprout extract powders are extremely hygroscopic and the preparation of

capsules containing accurate doses by weight is challenging and very expensive. (3) Administration of GR as an oral precursor of SF results in highly variable conversions of GR to SF metabolites (dithiocarbamates) among individuals, ranging from 1 – 40%, but fairly consistent between individuals (17,27,30-32).

In this study in healthy former smokers, BSP will be provided in the form of the commercially available dietary supplement, Avmacol®. Although a number of dietary supplements containing GR have been available in the U.S. market for several years now, Avmacol® is the first commercial product to contain GR plus the fully active enzyme myrosinase, thus yielding a higher and much more consistent SF dose upon ingestion. Avmacol® tablets contain only GR-rich broccoli seed extract, freeze-dried broccoli sprouts for the myrosinase source, and the inert excipients required to form a tablet. They are manufactured by Nutramax Laboratories, Inc. (Edgewood, Maryland, USA). Avmacol® has been sold as a nutritional supplement in the United States since 2013, and is manufactured under GMP standards, which has a shelf life of two years at ambient temperature. Based on previous human studies with both dietary and topical broccoli sprout extracts, and related broccoli seed preparations, and the absence of severe or serious risks (no Grade II toxicities have been observed in > 500 patients) (see Table 3 in Clinical Protocol), we do not anticipate serious adverse events to be associated with the administration of Avmacol® to study participants in this proposed trial.

4.1.2. Description of Origin of Sulforaphane, Purification, and Stabilization

Sulforaphane (SF) and its precursor GR are naturally occurring substances (phytochemicals) found in cruciferous vegetables. For many years now, the only reliable source of SF for clinical trials was our own broccoli sprout extract preparation. Whereas glucoraphanin has in recent years been made available in the supplement market by a number of manufacturers, SF has continued to elude commercialization. Now, with the introduction of Avmacol® to the dietary supplement market, a vetted, stable source of SF is available to clinical trial participants, and could be purchased by them or by others, even after their involvement in clinical studies ends. This is something that has not been possible with previous SF-rich broccoli sprout extract preparations.

The biologically active phytochemical in Avmacol® is glucoraphanin (GR; 4-methylsulfinylbutyl-glucosinolate), the precursor of sulforaphane (1-isothiocyanato-(4*R*)-(methylsulfinyl)butane). Sulforaphane (SF) is the aglycone breakdown product of the GR. The molecular formula of SF is C₆H₁₁NOS₂, and its molecular weight is 177.29 daltons. The structural formulae of GR and SF are shown in **Figure 1**. After ingestion and absorption, SF is conjugated with glutathione by glutathione-S-transferases (GSTs), then metabolized sequentially by γ -glutamyltranspeptidase (GTP), cysteinylglycinase (Cgase), and N-acetyltransferase (NAT) to form mercapturic acids, the predominant metabolites of SF found in urine (**Figure 2**) (26,27,31).

Figure 1. The Structural Formulae of Glucoraphanin and Sulforaphane

[figure not shown]
[figure not shown]

[figure not shown]
Figure 2. Metabolism of Glucoraphanin in Humans

Sulforaphane conjugates quickly accumulate in various types of cells in culture, reaching intracellular concentrations in the millimolar (mM) range (33). Intracellular accumulation is achieved through conjugation with cellular glutathione (34), a reaction that is accelerated by glutathione S-transferases (35), and the glutathione conjugate is then exported by a transporter-mediated mechanism (36). SF activates the Nrf-2 pathway resulting in elevated gene transcription via the Antioxidant-Response Element in the regulatory domain of its target genes (28).

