4.1.5.3 Broccoli sprout extract with daikon

Egner et al. conducted a cross-over clinical trial in Qidong, China in 2009 to compare the bioavailability and tolerability of SF from beverages made with two sprouted broccoli seed powders: one glucoraphanin-rich (GR-rich) powder and the other sulforaphane-rich (SF-rich) powder. SF was either generated *in vivo* from the GR contained in the GR-rich powder by gut microflora or formed by *ex vivo* treatment of GR-rich powder with myrosinase from daikon (*Raphanus sativus*) seeds to generate SF-rich powder. Fifty healthy, eligible participants were requested to refrain from crucifer consumption and randomized into two treatment arms. The study design was

as follows: 5-Day run-in period, 7-Day administration of beverages, 5-Day washout period, and 7-Day administration of the opposite intervention. Isotope dilution mass spectrometry was used to measure levels of GR, SF and SF thiol conjugates in urine samples collected daily throughout the study. Bioavailability, as measured by urinary excretion of SF and its metabolites (in approximately 12 hour collections after dosing), was substantially greater with the SF (mean = 70%) than with GR-rich (mean = 5%) beverages. The primary urinary metabolite of following administration of either GR-rich or SF-rich powder was the acetylcysteine conjugate of SF. Inter-individual variability in excretion was considerably lower with the SF-rich than GR-rich beverage. Elimination rates were considerably slower with GR-rich beverages allowing for achievement of steady state dosing as opposed to bolus dosing with SF-rich beverages. Results from this trial led us to consider blends of SF and GR as SF-rich and GR-rich mixtures to achieve peak concentrations for activation of some targets and prolonged inhibition of others implicated in the protective actions of SF. The Avmacol® to be administered during this trial follows this pharmacokinetic principle, as the bioactive ingredients include broccoli seed powder, containing both GR and myrosinase which is responsible for consistent *in vivo* delivery of 40% of the GR content as SF (46).

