Trace	22	663	2.58 (1.43-4.66)
Mild	37	493	5.04 (2.94-8.62)
Moderate/severe	16	315	3.20 (1.65-6.23)
P for trend			<0.0001

* Adjusted for age, sex, years of cigarette smoking, and number of cigarettes per day.

The presence of mild, moderate or severe radiographic emphysema on the LDCT scans at baseline was significantly associated with a 3- to 5-fold increased risk of developing lung cancer compared to smokers without emphysema (61).

We will recruit subjects for the present study from the existing PluSS participants who had mild, moderate or severe emphysema or GOLD II-IV COPD. Among the original PluSS participants who, as of 12/31/2015, were <75 years old, alive, free of cancer, and had quit smoking within the past 15 years, 356 had GOLD II-IV COPD (with or without emphysema), and additional 167 with mild, moderate or severe emphysema (without COPD). All these 523 subjects are potentially eligible for the proposed study. Based on our previous experience in the Iloprost study (22), which used a very similar protocol as the one proposed here, there was a 20% recruitment rate. Thus, we expect to fulfill our recruitment goal of at least 72 former smokers into the study within the first 3 years of the proposed study. With a 20% dropout rate based on our previous experience (22), we expect to have 60 study subjects who will complete the entire course of the trial.

If the proposed chemopreventive agent is effective, it will bring beneficial effect for study participants on reducing their risk of lung cancer. After the end of the study, all study participants can conduct their oral intake of Avmacol® since this dietary supplement is relatively cheap and commercially available.

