5.5 Clinical Visits

Besides two clinical visits in stage 1 of the study for eligibility screening, all eligibility study participants will begin taking the study tablets at visit 1 of stage 2 of the study and return to the study clinic at the end of months 3, 6, 9, and 12 (the end of treatment period). At each clinical visit, the clinical research nurse/assistant will conduct the following:

- 1) Exam the subject's diary for dosing and timing of intake of test tablets, and keep the diary in subject's folder.
- 2) Count and record the remaining tablets given.
- 3) Provide new study tablets that will supply the next 3 months.
- 4) Study participant will turn in the self-administered questionnaire for recording his/her intake of cruciferous vegetables in the past 3 months using a dietary frequency questionnaire (Appendix 5).
- 5) Collect blood, spot urine and nasal brushing samples
- 6) Conduct pulmonary function test: FEV1/FVC
- 7) Collect safety and toxicity measures at each clinical visit (once every 3 months) during the 12-month treatment period:
 - a) Collect adverse events (AEs) using the AE Recording Form (Appendix 8)

- b) Conduct physical examination including body weigh, height, and vitals by a registered nurse and record the results in the patient's study file
- c) Laboratory evaluation: CBC with platelets and differential, chemistry panel including liver function testing.
- 8) Only at the end of treatment period, bronchoscopy will be performed on the patient using the same procedure as described above in 5.1(8) and bronchial biopsies and lavage samples collected (stage 2- visit 5).

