Sample size consideration. In the iloprost trial, 57 former smokers were randomized to receive oral iloprost or placebo for 6 months. Treatment effects (adjusted for baseline levels) were statistically significant ($P \leq 0.01$) for all 3 endpoints (dysplasia index, average dysplasia score, worst dysplasia score). Anticipating a 20% dropout rate over 12 months, we will randomize at least 72 study subjects to ensure that 60 subjects complete our SF study. Assuming an average baseline dysplasia index of 22% and post-therapy 11% for subjects receiving SF, a simulation with 10,000 trials with a sample size of 60 subjects has yielded an 80% statistical power to detect a statistically significant (two-sided $p < 0.05$) treatment effect, using generalized linear models (binomial family, 6 biopsies) after controlling for baseline levels of DI. Calculations are similar for other endpoints, and actual power should be greater than the DI measure because they are continuous measures and have observed within-subject correlation (i.e., repeated measures).

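### Off-study sulforaphane supplements are neither barred nor asked about in the visible procedures, and no analysis uses the planned urine assays to detect their use in the placebo arm

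*Combined protocol and SAP*

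**What the plan says.** **Availability.** Section 4.1.1 states that "a number of dietary supplements containing GR have been available in the U.S. market for several years now" and that the study product has been sold in the United States since 2013. Section 4.1.2 adds that "a vetted, stable source of SF is available to clinical trial participants, and could be purchased by them or by others". Section 4.2 notes that "this dietary supplement is relatively cheap and commercially available".

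**Entry and conduct rules.** Section 3.2 opens with "Patients are not eligible if any one of the following conditions exists" and lists ten conditions. None concerns supplements, and nor does any criterion in 3.1. The treatment plan (5.3) and visit procedures (5.5) give no instruction to avoid such products. Section 5.6 names noncompliance as a reason for withdrawal, but no stated rule would be broken by supplement use.

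**Exposure records.** The instruments described are a tablet diary, a tablet count and a diet form: "Study participant will turn in the self-administered questionnaire for recording his/her intake of cruciferous vegetables in the past 3 months". The study calendar (Section 6) labels the diet form as a compliance item and shows no supplement or concomitant-medication log.

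**Urine.** Section 8.1.6 plans spot urine at months 0, 3, 6, 9 and 12, with no restriction to one arm. Two assays are planned: total isothiocyanates (ITC), as a measure of crucifer intake, and the N-acetylcysteine conjugate of SF (SF-NAC), as a check on study-tablet intake.

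**Analysis.** Section 9 does not mention either assay. The sample size makes no allowance for SF use in the placebo arm.

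**The concern.** The placebo arm is the only control for the histology, proliferation, apoptosis and gene expression comparisons. Participants are former smokers who know they are at high risk of lung cancer, and they are testing a product that anyone can buy. If some of the placebo arm take it, or something like it, the contrast shrinks toward zero. A null result would then be hard to read, because lack of effect and dilution would look alike. That matters in a proof-of-principle trial meant to inform whether SF is developed further.

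The gap is more than missing detail. Staff who followed the visible text exactly could randomise a current user of the study product, and would have no stated reason to ask about, or discourage, its use by a placebo participant.

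**Working it through.** **Inputs from the plan (9.1, 5.2).** The test is for a "statistically significant (two-sided $p < 0.05$) treatment effect". For power, "a simulation with 10,000 trials with a sample size of 60 subjects has yielded an 80% statistical power". The dysplasia index (DI) is 22% at baseline and 11% after SF, with six biopsies per subject. Allocation is 1:1, so there are 30 completers and 30 × 6 = 180 biopsies per arm.

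**Assumptions not in the documents.** Placebo DI stays at 22% without outside use. Biopsies within a subject are treated as independent. A share *c* of placebo participants takes an outside product and gains a fraction *e* of the SF effect.

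**Formula.** Placebo DI is p₁ = 0.22 − c·e·0.11, SF DI is p₂ = 0.11, and p̄ is their mean. Then

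power = Φ{ [(p₁ − p₂)√180 − 1.96√(2p̄(1 − p̄))] / √(p₁(1 − p₁) + p₂(1 − p₂)) }.

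**Reproducing the stated figure (c = 0).** (0.11 × 13.416 − 1.96 × 0.5249)/0.5191 = 0.861, so power is 80.5%. A 10,000-trial simulation gives 81.1% with model-based and 81.4% with robust standard errors. The stated 80% is confirmed, and it assumes no outside use.

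**With outside use.** For example, at c = 20% and full effect: (0.088 × 13.416 − 1.96 × 0.5105)/0.5067 = 0.355, so power is 63.9%.

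| Placebo participants using | Effect gained | Placebo DI | Difference (points) | Power |
|---|---|---|---|---|
| 0% | – | 22.00% | 11.00 | 80.5% |
| 5% | full | 21.45% | 10.45 | 76.9% |
| 10% | full | 20.90% | 9.90 | 72.9% |
| 20% | full | 19.80% | 8.80 | 63.9% |
| 10% | half | 21.45% | 10.45 | 76.9% |
| 20% | half | 20.90% | 9.90 | 72.9% |

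Simulation agrees with the full-effect rows to within one point. Restoring 80% power at full effect would need 33, 36 or 44 completers per arm at 5%, 10% or 20% use, against 30 planned.

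**How plausible full effect is.** Section 4.1.5.5 puts bioavailability at roughly 10% without active myrosinase and about 40% with it, a ratio of 10/40 = one quarter. Section 4.1.1 describes the study product as the first commercial one with fully active myrosinase. Full effect is therefore an upper bound for products without active myrosinase, but it is attainable with the study product at the study dose.

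**What urine can show.** Section 4.1.5.4 reports excretion back at baseline by 72 hours after crucifer intake. Visits are about 90 days apart, so a spot sample reflects roughly the last 3 of 90 days. Regular use should show, and intermittent use can be missed. A raised value alone does not separate a supplement from broccoli.

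**The case against.** The strongest reply is that exposure is measured. A reader might infer from the visit list that nothing records outside use and that any dilution would go unseen. Section 8.1.6 does not support that. SF-NAC and total ITC are planned at five time points in both arms, a placebo participant taking the product regularly would be expected to show SF-NAC, and the month-0 sample could reveal a current user. What remains is narrower: SF-NAC is described only as a check on study tablets, the window is short, and no analysis uses the result.

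A reader might also infer from 4.1.2 and 4.2 that the plan contemplates purchase during the trial. It does not say so. The sentence in 4.2 concerns use after the study, and the one in 4.1.2 goes on to stress availability after participation ends. They establish only that the product is on sale and, in 4.2, cheap.

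The consent form, screening form, medical history, diet questionnaire and tablet log are not in the text, and any of them might carry a supplement question or an instruction. That limits the claim to the visible procedures.

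The size is open to challenge as well. No rate of use is given, and full effect implies buying the equivalent of eight tablets a day for about a year. The half-effect rows answer this in part.

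The earlier crossover trial in 4.1.5.3, where "Fifty healthy, eligible participants were requested to refrain from crucifer consumption and randomized into two treatment arms", is a weak precedent. It had 7-day dosing periods and urinary metabolites as the outcome, so diet bore directly on the measurement.

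**Conclusion.** The point holds in limited form. The visible criteria, treatment plan and visit procedures neither exclude nor ask about outside glucoraphanin or SF supplements, and Section 9 does not use the planned urine assays to detect or handle their use in the placebo arm. The documents do not support the stronger reading that such use would be wholly unrecorded, and they give no evidence that it will be common.

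The possible loss is from 80.5% power to about 77%, 73% or 64% if 5%, 10% or 20% of placebo participants gain the full effect. At half effect it is about 77% at 10% use and 73% at 20%. These figures rest on assumed rates of use, a placebo DI that otherwise stays at 22%, and independent biopsies. They illustrate sensitivity and are not a forecast. This is a cheap improvement, not a flaw that invalidates the design.

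**What to change.** 1. Section 3.2: add an exclusion for current use of any glucoraphanin, sulforaphane or broccoli-extract supplement, including the study product.
2. Section 5.3: add an agreement not to take such supplements, other than the study tablets, until the month-12 bronchoscopy. Ordinary vegetable intake can stay unrestricted.
3. The three-monthly questionnaire (Appendix 5): add one line on supplement use, unless it already has one.
4. Section 9: prespecify a report, after database lock, of placebo-arm contamination from the SF-NAC assays already planned, read alongside the supplement and crucifer answers. The randomised comparison stays primary.

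The cost is a short amendment and one questionnaire line, with no new visit, sample or assay. The downside is that a few current supplement users become ineligible.
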